# 342 13.2 Patient recruitment and drop-out status

- 343 The status of patient recruitment and drop-out will be summarized and listed. Comparison of
- 344 the overall elimination/drop-out rate between the two groups will be performed with Chi-
- 345 Square test.

#### 346 13.3 Demographics and baseline characteristics

- 13.3.1 Demographics and baseline data will be presented.
- 348 13.3.2 For between-group differences, numeric variables will be analyzed using independent-
- samples t test or Mann-Whitney U test; categorical variables will be analyzed using the chi-
- square test, continuity correction chi-square test or Fisher exact test.

## 351 13.4 Intra- and postoperative variables

- Numeric variables will be analyzed using the independent-samples t tests or Mann-Whitney U
- 353 tests; categorical variables will be analyzed using the chi-square tests, continuity correction
- 354 chi-square tests or Fisher exact tests. Missing data will not be replaced.

#### 355 13.5 Efficacy analysis

356 13.5.1 Evaluation of primary endpoints

- For the primary outcomes (maternal pain intensity and sedation score immediately after fetal
- delivery), the differences between group will be analyzed using Mann-Whitney U test. Median
- differences and 95% CIs will be calculated with the Hodges-Lehmann estimators.
- 360 13.5.2 Evaluation of secondary and other endpoints
- 361 13.5.2.1 Discrete variables (maternal pain intensity and sedation score during the perinatal
- period, neonatal Apgar scores, and umbilical vein pH) will be analyzed with the Mann-Whitney
- 363 U tests. Median differences and 95% CIs will be calculated with the Hodges-Lehmann
- 364 estimators. Missing data will not be replaced.
- 13.5.2.2 Categorical variables (neonatal ward admission proportion) will be analyzed using the
- chi-square tests, continuity correction chi-square tests or Fisher exact tests. The rate differences
- and 95% CIs will be provided. Missing data will not be replaced.
- 368 13.5.2.3 Time-to-event variables (length of hospital stay after surgery) will be analyzed with
- the Kaplan-Meier estimators with differences between groups assessed by the log-rank test;
- Cox proportional hazards models will be used to calculate HRs and 95% CIs.
- 371 13.6 Safety analysis
- 372 13.5.1 Describe the occurrence of adverse events in each group.
- 13.5.2 Describe the management of adverse events when appropriate.
- 374 13.5.3 Describe the occurrence of severe adverse events.
- 375 13.5.4 The rates of adverse events and/or managements between the two groups will be
- compared with Chi-Square test, continuity correction Chi-Square test or Fisher exact test.
- 377 13.5.5 Missing data will not be replaced.

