#### 3.2 Sample size calculation

Based on a pilot study, we suppose that the mean difference in NRS pain score immediately after fetal delivery (10 min after administering esketamine) would be 0.3 with standard deviations (SD) of 0.85 and 1.23, respectively, between the two groups. With alpha set at 5% and power at 90%, 263 patients will be needed in each group. Considering a drop-out rate of about 10%, we plan to enroll 300 patients in each group. The sample size was estimated with the PASS 15.0 software.

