# 329 13.1 General principles

- 330 13.1.1 The primary and secondary outcomes will be analyzed in an intention-to-treat
- population, i.e., all patients are analyzed in the group to which they are randomized. Also, we
- will do per-protocol analysis for the primary endpoints after excluding patients with major
- 333 protocol deviation.
- 334 13.1.2 For continuous variables, the Kolmogorov-Smirnov test will be applied to evaluate the
- distribution. Variables with normal distribution were presented as mean  $\pm$  standard deviation
- 336 (SD). Variables with non-normal distribution will be presented as median and interquartile
- 337 range (IQR).
- 13.1.3 Categorical variables will be presented as number of cases (%).
- 13.1.4 For the primary outcomes, p<0.025 (0.05/2) will be considered statistically significant.
- For other outcomes, two-tailed tests will be used and p<0.05 will be considered to be
- statistically significant unless otherwise indicated after Bonferroni correction.

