# 4.4 Intra- and postoperative variables

- Numeric variables will be analyzed using the independent-samples t tests or Mann-Whitney U
- tests; categorical variables will be analyzed using the chi-square tests, continuity correction

- 554 chi-square tests or Fisher exact tests. Missing data will not be replaced.
- 555 **4.5 Efficacy analysis**
- 556 4.5.1 Evaluation of primary endpoints
- For the primary outcomes (maternal pain intensity and sedation score immediately after fetal
- delivery), the differences between group will be analyzed using Mann-Whitney U test. Median
- differences and 95% CIs will be calculated with the Hodges-Lehmann estimators.
- 560 4.5.2 Evaluation of secondary and other endpoints
- 4.5.1 Discrete variables (maternal pain intensity and sedation score during the perinatal period,
- neonatal Apgar scores, and umbilical vein pH) will be analyzed with the Mann-Whitney U tests.
- Median differences and 95% CIs will be calculated with the Hodges-Lehmann estimators.
- Missing data will not be replaced.
- 4.5.2 Categorical variables (neonatal ward admission proportion) will be analyzed using the
- chi-square tests, continuity correction chi-square tests or Fisher exact tests. The rate differences
- and 95% CIs will be provided. Missing data will not be replaced.
- 4.5.3 Time-to-event variables (length of hospital stay after surgery) will be analyzed with the
- Kaplan-Meier estimators with differences between groups assessed by the log-rank test; Cox
- proportional hazards models will be used to calculate HRs and 95% CIs.
- 571 4.6 Safety analysis

- 4.6.1 Describe the occurrence of adverse events in each group.
- 573 4.6.2 Describe the management of adverse events when appropriate.
- 4.6.3 Describe the occurrence of severe adverse events.
- 575 4.6.4 The rates of adverse events and/or managements between the two groups will be
- 576 compared with Chi-Square test, continuity correction Chi-Square test or Fisher exact test.
- 577 4.6.5 Missing data will not be replaced.

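### The only planned primary effect estimate (Hodges-Lehmann) moves in whole or half points on the integer NRS, so it cannot express the 0.3-point mean difference the trial is sized on

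*Combined protocol and SAP*

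**What the plan says.** Protocol 13.5.1 covers the two co-primary outcomes, NRS pain and Ramsay sedation immediately after delivery. Its key words are "delivery), the differences between group will be analyzed using Mann-Whitney U test. Median". SAP 4.5.1 repeats the rule: "differences and 95% CIs will be calculated with the Hodges-Lehmann estimators". No other effect measure is planned for these outcomes.

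SAP 3.1 describes the NRS as an 11-point scale (0 to 10) and the Ramsay scale as six grades (1 to 6).

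Section 3.2 states the planning effect as a mean difference that "would be 0.3 with standard deviations (SD) of 0.85 and 1.23, respectively, between the two groups". It does not say which arm has which SD, and it gives neither a baseline mean nor a score distribution.

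For descriptive summaries, 13.1.2 adds: "Variables with non-normal distribution will be presented as median and interquartile" range. Section 13.1.4 sets p<0.025 for each primary outcome.

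**The concern.** The effect the trial is built to detect and the number it will report are on different footings. Sizing uses a difference in means, which can be 0.3. The reported estimate is the median of all between-arm pairwise differences of integers, which cannot be 0.3. If the drug does what was assumed, the headline table is likely to set a small p-value beside a difference of 0, or less often 1.

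A reader could take the 0 as no effect, or the 1 as more than three times the planned effect. The authors could also be pushed into choosing a different estimate after unmasking. The descriptive rule does not help. Median and IQR are just as coarse, and mean and SD appear only if a Kolmogorov-Smirnov test accepts normality, which is implausible for heavily tied integers at this sample size.

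**Working it through.** **1. Inputs.** From section 3.2: mean difference 0.3, SDs 0.85 and 1.23, alpha 5% (taken as two-sided), power 90%, 263 per group, 300 enrolled per group. From 13.1.4: p<0.025. From SAP 3.1: integer scales. Assumed, because the documents are silent: the shape of the scores, the baseline mean, and which arm has which SD. Differences below are esketamine minus control.

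**2. The plan's own figure.** The plan states: "With alpha set at 5% and power at 90%, 263 patients will be needed in each group".
- Normal approximation: n = (1.960 + 1.282)² × (0.85² + 1.23²) / 0.3² = 10.507 × 2.2354 / 0.09 = 261.
- The unequal-variance t version gives 263, as stated.
- With 10% drop-out, 263 / 0.9 = 292.2, so 293. The plan rounds this to 300.

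**3. The exact part.** With 300 per arm there are 300 × 300 = 90,000 pairwise differences, all integers. Their median is the mean of the two middle values, so it is a whole or half number. The usual 95% limits are the ordered differences near ranks 45,000 ± 1.96 × √(90,000 × 601 / 12) = 45,000 ± 4,161, that is about ranks 40,840 and 49,160. These limits are whole numbers. The estimate is 0 whenever fewer than half the pairs favour either arm. The interval is exactly 0 to 0 whenever tied pairs cover both ranks.

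**4. Two constructed data sets, SDs about 0.8 and 1.2.**

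| | A (near the floor) | B (away from it) |
|---|---|---|
| Control counts, score 0 upward | 214, 43, 20, 11, 6, 3, 2, 1 | 22, 56, 93, 81, 38, 9, 1 |
| Esketamine counts, score 0 upward | 252, 27, 11, 5, 3, 1, 1 | 9, 71, 140, 71, 9 |
| Control mean | 174/300 = 0.58 | 688/300 = 2.29 |
| Esketamine mean | 87/300 = 0.29 | 600/300 = 2.00 |
| Pairs lower on esketamine | 23,168 | 39,822 |
| Tied pairs | 55,387 | 23,287 |
| Pairs higher on esketamine | 11,445 | 26,891 |
| Ranks held by ties | 23,169 to 78,555 | 39,823 to 63,109 |
| Hodges-Lehmann (95% CI) | 0 (0 to 0) | 0 (0 to 0) |
| Tie-corrected Mann-Whitney p | 0.00015 | 0.0015 |
| (Lower pairs + half of ties) / 90,000 | 0.565 | 0.572 |

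**5. How often this happens.** I simulated 300 per arm, 3,000 trials in each of 45 scenarios. Scores were clipped-rounded normal, beta-binomial, negative binomial or zero-inflated Poisson. Esketamine means ran from 0.1 to 5, the true mean difference was 0.3, and both SD assignments were used where a fit exists. The middle two columns are among trials with p<0.025.

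| Larger SD in | Estimate 0, CI containing 0 | CI containing 0 | Trials with p<0.025 |
|---|---|---|---|
| Control (26 scenarios) | 98.4-100% | 100% | 46-100% |
| Esketamine (19 scenarios) | 41-100% | at least 94% | at least 86% |

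Containing 0 includes intervals with a limit at 0. The lowest values in the second row (41% and 47%) arise with clipped-normal scores at esketamine means of 0.8 and 1.0, where the estimate is otherwise −1 and rarely −0.5. With the larger SD in control, the chance that an esketamine woman scores lower than a control woman is at most 0.446. That is below one half, so the median pairwise difference stays at 0. Runs at 263 per group gave the same picture.

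**6. What other measures would show.** The standard error of the mean difference is √((0.85² + 1.23²) / 300) = 0.0863. A planned-size effect then reads −0.30, with 95% CI −0.47 to −0.13 and 97.5% CI (multiplier 2.241) −0.49 to −0.11. The Mann-Whitney probability would be about 0.55 to 0.58 with the larger SD in control.

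**7. Ramsay, illustration only.** Assume 5% of control women score 3 and the rest score 2. If 40% of esketamine women score 3, the share of pairs higher on esketamine is 0.40 × 0.95 = 0.38 and the estimate is 0. At 60% the share is 0.60 × 0.95 = 0.57 and the estimate is 1. The output switches when the share passes one half.

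**The case against.** Hodges-Lehmann is the customary partner of the Mann-Whitney test and targets a location shift, not a mean, so failing to equal 0.3 might be called a difference of estimand. That is fair as far as it goes. But the pairing rests on a continuous shift model, whereas these scores are heavily tied and the plan itself assumes unequal SDs. The plan also frames its target as a mean. For larger effects the measure does respond: in simulation it settled on 1 at true differences of 0.8 to 1.0.

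Three stronger readings are tempting, and the documents do not support them.
- A reader might infer that a planned-size effect is bound to appear as a significant p-value beside 0 (0 to 0). The SD assignment and score distribution are not given, and significance itself is not assured. In rounded-normal checks with assumed esketamine means of 0.5 to 3, that exact combination occurred in about 2-61% of trials. It becomes more frequent only as scores crowd at zero.
- A reader might infer that the sedation effect cannot be quantified either. No sedation effect is stated, and step 7 shows the answer turns on assumed proportions.
- A reader might infer that the primary test is compromised. It is not.

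The mean difference also has limits. Suppose all esketamine women score 0. If 30% of controls score 1, or 6% score 5, the mean difference is 0.3 both times. The Mann-Whitney probability does separate them: 0.30 + 0.70/2 = 0.65 against 0.06 + 0.94/2 = 0.53. In simulations with the larger SD in control, a Welch 95% interval excluded 0 while the Mann-Whitney p was at least 0.025 in 6-48% of trials, partly because 95% intervals are set beside a 0.025 threshold.

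Finally, nothing is lost for good, since the same records yield every alternative. That stands, and it lowers the stakes. It does not remove the advantage of naming the measure before unmasking.

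**Conclusion.** The concern holds for pain. That the estimate cannot be 0.3 is exact and needs no simulation. That it will read 0 at the planned effect is very likely but not certain. It is close to universal among significant trials if control has the larger SD. If esketamine has it, the frequency depends on the baseline, and the usual alternative is a full point. In both cases the interval nearly always includes 0. These frequencies rest on assumed distributions and baseline means.

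For sedation the coarseness is the same, but it matters only if the shift is under about one point, which the documents leave open. The defect is one of estimation and reporting. No significance decision changes.

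**What to change.** Keep the Mann-Whitney test. In protocol 13.5.1 and SAP 4.5.1:

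- Name the Mann-Whitney probability as the lead effect measure: P(better on esketamine) plus half P(tie). Define the favourable direction for each scale (for pain, the lower score). Give a 97.5% CI to match the p<0.025 threshold.
- For NRS, also report the mean difference with a Welch or bootstrap CI, since this is the quantity used for sizing. Note that it may not always agree with the rank test.
- Show the number of women at each score by arm, for both NRS and Ramsay.
- Keep Hodges-Lehmann as a supplementary line.

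The cost is a few lines of wording and a few extra output rows. No new data and no change of test are needed. The wording should be settled before unmasking.

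### At the planned 0.3-point effect, a significant pain result would most likely be reported as a Hodges-Lehmann difference of 0 with an interval that includes 0, because the planned effect measure is not the one the trial was sized on

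*Combined protocol and SAP*

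**What the plan says.** **Sizing (Protocol 3.2, repeated in SAP 2).** The planning assumption for pain reads: "mean difference in NRS pain score immediately after fetal delivery (10 min after administering esketamine) would be 0.3". The SDs are given as 0.85 and 1.23, but the text does not say which group has which. On size and power it states: "With alpha set at 5% and power at 90%, 263 patients will be needed in each group". Allowing for about 10% drop-out, 300 per group are to be enrolled.

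**Scales (Protocol 7.1, SAP 3.1).** Pain is an 11-point NRS from 0 to 10. Sedation is the six-category Ramsay scale.

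**Test and effect measure (Protocol 13.5.1; SAP 4.5.1, evaluation of primary endpoints).** Both co-primaries are compared by Mann-Whitney U, and median "differences and 95% CIs will be calculated with the Hodges-Lehmann estimators". No mean difference, probability of superiority or other effect measure is planned for them.

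**Threshold (Protocol 13.1.4, SAP 4.1.4).** "For the primary outcomes, p<0.025 (0.05/2) will be considered statistically significant".

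**The concern.** The quantity that justified the sample size is a difference in means. The quantity to be reported is the median of all pairwise between-group differences. On integer scores every pairwise difference is an integer, so that median is an integer, or a half-integer if the two middle values differ. A shift of 0.3 falls between the available values.

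The likely headline for a successful pain comparison is therefore a p-value below 0.025 beside a difference of 0 and an interval such as 0 to 0 or 0 to 1. That looks contradictory and gives no usable size of effect. For an expected benefit as small as 0.3 points, readers will mainly want to judge whether it is large enough to matter, and this output would not let them.

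Separately, intervals at 95% do not correspond to a decision rule at 0.025.

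**Working it through.** **1. Reproducing the sample size.** Inputs from Protocol 3.2: difference 0.3, SDs 0.85 and 1.23, alpha 5% (taken as two-sided), power 90%.

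- Variance sum: 0.85² + 1.23² = 0.7225 + 1.5129 = 2.2354.
- Normal approximation: n = (1.960 + 1.282)² × 2.2354 / 0.3² ≈ 261 per group.
- Unequal-variance (Welch) noncentral t: 263 per group, the stated figure. One-sided 5% gives 213, which does not match.

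So the powered quantity is the difference in means, tested two-sided. After 10% drop-out, 300 per group leaves 300 × 0.90 = 270.

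**2. What Hodges-Lehmann can show.** With 270 × 270 = 72,900 pairs, the estimate is the midpoint of the two middle pairwise differences. It is 0 whenever fewer than half the pairs are below 0 and fewer than half are above 0. Take discretised-normal scores with control mean 1.0, esketamine SD 0.85 and control SD 1.23. For control minus esketamine, the pair probabilities are 0.375 above 0, 0.344 tied and 0.281 below 0. Both tails are well under one half, so the estimate is 0 although the means differ by 0.3.

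**3. Simulation.** Assumptions: integer scores 0-10; mean 0.3 lower on esketamine; 270 per group; 1,500 trials per scenario; discretised-normal (DN) or negative-binomial (NB) shapes; control mean 0.5 to 3.0; both SD assignments; tie-corrected Mann-Whitney; large-sample order-statistic interval. Shapes and means are assumed because the documents give no pilot distribution. The last three columns are among trials with p<0.025 in favour of esketamine.

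| Shape, control mean | SD esketamine / control | Power at 0.025 | Estimate = 0 | 95% CI 0 to 0 | 95% CI includes 0 |
|---|---|---|---|---|---|
| DN 0.5 | 0.85 / 1.23 | 98.4% | 100% | 100% | 100% |
| DN 1.0 | 0.85 / 1.23 | 44.1% | 100% | 99.4% | 100% |
| DN 2.0 | 0.85 / 1.23 | 72.9% | 99.2% | 56.1% | 100% |
| DN 3.0 | 0.85 / 1.23 | 83.2% | 97.6% | 50.9% | 100% |
| NB 1.0 | 0.85 / 1.23 | 53.9% | 100% | 99.6% | 100% |
| DN 0.8 | 1.23 / 0.85 | 100% | 90.2% | 30.4% | 99.8% |
| DN 1.2 | 1.23 / 0.85 | 99.8% | 43.6% | 2.1% | 96.5% |
| DN 3.0 | 1.23 / 0.85 | 83.3% | 97.0% | 48.4% | 100% |

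When the estimate was not 0 it was almost always 1. Repeat simulations gave lower ends of 97% for the first SD assignment and 39% to 50% for the reverse, hence about 97-100% and about 40-100%.

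**4. Sedation.** The documents give no effect size or SD. I assumed control scores of 1, 2 and 3 in 5%, 93% and 2%. If 10% to 40% of esketamine patients score 3 or more, power at 0.025 is 98% to 100% and the estimate is 0 in 99.6% to 100% of all trials. At 50% it is 0 in 29%, at 55% in 1%, and at 60% or more it was never 0.

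**5. Interval level.** The level matching 0.025 is 97.5%. For a mean difference at 270 per group, SE = √(2.2354/270) = 0.0910. Half-widths are 1.960 × 0.0910 = 0.178 at 95% and 2.241 × 0.0910 = 0.204 at 97.5%, a ratio of 1.14. For the Hodges-Lehmann interval on pain, the 95% and 97.5% limits were identical in 88% to 100% of trials.

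**The case against.** Mann-Whitney is a sound choice for skewed, heavily tied ordinal scores, and Hodges-Lehmann is its customary companion. Type I error is unaffected and the decision rule works. The plan also provides median and IQR for non-normal variables, so some description would be given. All of this stands, and there is no need to replace the test. But group medians of such scores may tie as well, so they do not reliably supply the missing effect size.

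Stronger readings are tempting, and the documents do not support them:

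- **That the pain estimate is bound to read 0.** This depends on the score distribution, which is not given, and on which group has which SD, which is not stated. With the SDs reversed, the estimate was 1 in more than half of positive trials in the least favourable scenarios.
- **That the same holds for sedation.** Nothing in the documents fixes the size of that shift. If clearly more than half of esketamine patients become drowsy, the estimate reads 1.
- **That the 95% interval will often exclude 0 when 0.025<p<0.05.** For a mean difference this would happen in about 5.5% of trials at the design assumptions (90.9% power at 0.05 less 85.4% at 0.025, normal approximation). For the interval actually planned it hardly arises: among about 295 simulated pain trials with p in that range, none had a 95% Hodges-Lehmann interval excluding 0.

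The sizing at 5% against testing at 0.025 is a separate matter and adds no weight here.

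**Conclusion.** The point holds, as a should-fix weakness in reporting. For pain at the planned effect, the only planned effect measure can, and most likely will, read 0, and its interval will include 0 in at least 96% of significant trials under either SD assignment. The share of significant trials with an estimate of exactly 0 is about 97-100% with esketamine SD 0.85 and control SD 1.23, and about 40-100% with the SDs reversed. These figures rest on integer recording, 270 evaluable per group, a true mean difference of 0.3, and assumed score shapes and control means.

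The 95% versus 0.025 mismatch is real in the text, but it seldom alters the printed Hodges-Lehmann limits. It matters for the measures that should be added.

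The stated 90% power belongs to a test of means. Mann-Whitney power at 0.025 ran from 43% to 100% across the scenarios, so the sample-size section does not describe the planned test.

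**What to change.** In Protocol 13.5.1 and SAP 4.5.1, before unmasking:

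- Keep Mann-Whitney U as the primary test. The Hodges-Lehmann difference may stay as a supporting figure.
- For pain, add the difference in mean NRS with a 97.5% CI (Welch or bootstrap), the quantity the trial was sized on.
- For both co-primaries, add the probability of superiority (the chance that a randomly chosen esketamine patient scores better on pain, or higher on sedation, than a control patient, with ties counted as half) with a 97.5% CI, and tabulate the score distribution by group.
- Use 97.5% rather than 95% intervals for the co-primaries.

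In Protocol 3.2 and SAP 2, state that the calculation is for a mean-difference test and not for Mann-Whitney, and say which group has which SD.

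The cost is a few more lines of analysis and no new data. Mean-difference intervals are about 14% wider than at 95% (half-width 0.204 against 0.178 points), and a mean is reported for an ordinal pain score, as the sample-size calculation already does. No mean is asked for on the Ramsay scale.

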## 1. Background

 Epidural anesthesia is widely used for cesarean delivery, especially in China. However, due to incomplete block of the splanchnic nerve, parturients often complain discomfort or pain during exploration of the uterus, pulling peritoneum, and fetal delivery. The referred pain brings painful memories and mental stress to parturients, and also affect the conduct of surgical procedure. In some cases, change to general anesthesia is required. Therefore, supplemental analgesics during cesarean delivery under epidural anesthesia is sometimes required and necessary.

Esketamine, a dextrorotatory isomer of ketamine, is two times more potent than ketamine in hypnotic and analgesic effect, with less psychiatric adverse reactions. In a pre-clinical study, Strümper et al. verified that esketamine has similar effects on uterine perfusion, and has limited effects on maternal/fetal hemodynamics and respiration when compared with racemic ketamine; it thus might be an appropriate analgesic in the obstetric setting. In clinical studies, Unlugenc et al. found that adding esketamine (0.05 mg/kg) to intrathecal plain bupivacaine (10 mg) for spinal anesthesia resulted in rapid onset of sensory and motor block and enhanced segmental spread of spinal block in patients undergoing cesarean delivery. Suppa et al. reported that, for women after cesarean delivery, preventive esketamine administration (0.5 mg/kg intramuscular injection at 10 minutes after childbirth, followed by a 2 μg/kg/min intravenous infusion for 12 h) has analgesic effects and was safe.

However, the efficacy and safety of intravenous esketamine before childbirth are still unclear. We therefore try to investigate the sedative and analgesic effects of intravenous esketamine before childbirth during cesarean delivery under epidural anesthesia. We will also explore the placental transfer of intravenous esketamine as well as the effects on maternal and fetal outcomes.

[figure not shown]

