# 251 8.1 Primary outcome

- Our co-primary outcomes include maternal pain intensity and sedation score immediately after
- fetal delivery (about 10 min after esketamine). Pain intensity will be assessed with the NRS.

- 254 Maternal sedation level will be assessed with the Ramsay Sedation Scale.
- 255 **8.2 Secondary outcomes**
- 8.2.1 Maternal pain intensity as assessed with the NRS at the following timepoints: surgical
- 257 incision (2 min after study drug administration), 5 min after study drug administration, end of
- surgery, 6 h after surgery, and 12 h after the surgery.
- 8.2.2 Maternal sedation level as assessed with the Ramsay Sedation Scale at the following
- 260 timepoints: surgical incision (2 min after study drug administration), 5 min after study drug
- administration, end of surgery, 6 h after surgery, and 12 h after the surgery.
- 262 8.2.3 Neonatal Appar score assessed at 1 and 5 minutes after birth.
- 263 8.2.4 Postnatal umbilical vein blood gas pH value.
- 264 8.3 Other outcomes
- 8.3.1 Mean blood pressure (MBP), heart rate (HR), and pulse oxygen saturation (SpO2)
- 266 measured before anesthesia, immediately after anesthesia, surgical incision (2 min after study
- drug administration), 5 min after study drug administration, immediately after fetal delivery
- 268 (10 min after study drug administration), end of surgery, and 1 h after surgery.
- 269 8.3.2 The requirement of neonatal ward admission and length of hospital stay.
- 270 8.3.3 Plasma concentrations of esketamine in maternal blood, neonatal umbilical venous blood
- and umbilical arterial blood after birth.

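### The planned Apgar summaries (Hodges-Lehmann difference, median and IQR) cannot show an excess of low scores; add counts per score and a risk difference at one pre-fixed cut-off

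*Combined protocol and SAP*

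**What the plan says.** Apgar is a secondary outcome, "assessed at 1 and 5 minutes after birth" (protocol 8.2.3; SAP 3.2.3). Protocol 13.5.2.1 classes it as a discrete variable, together with pain, sedation and cord pH, and names the test: "period, neonatal Apgar scores, and umbilical vein pH) will be analyzed with the Mann-Whitney". The effect measure is a Hodges-Lehmann estimate of the difference with a 95% CI. The SAP has the same rule: "neonatal Apgar scores, and umbilical vein pH) will be analyzed with the Mann-Whitney U tests". There it is the second item numbered 4.5.1, under heading 4.5.2.

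The only descriptive rule that seems to reach a score of this kind is in protocol 13.1.2: "Variables with non-normal distribution will be presented as median and interquartile" range. For outcomes other than the co-primaries, protocol 13.1.4 sets the threshold: "For other outcomes, two-tailed tests will be used and p<0.05 will be considered to be" significant, subject to a Bonferroni proviso.

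Neither document defines a low Apgar score or plans a proportion or risk difference for one. The predicted adverse events in protocol 9.2 include no low-Apgar event. The one neonatal outcome handled as a proportion, with a rate difference and 95% CI, is ward admission (protocol 13.5.2.2).

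**The concern.** The Background gives as a reason for the trial that "the efficacy and safety of intravenous esketamine before childbirth are still unclear", and says that fetal outcomes will be explored. Study drug is given about 10 minutes before delivery. Eligibility is limited to full-term, single, elective deliveries without severe obstetric complications, so most newborns would be expected to score near the top. Harm from the drug would then show as a few more newborns in the lower tail.

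A median, an IQR and a Hodges-Lehmann shift all describe the centre of the distribution. If the centre is the same in both arms, they agree whatever happens in the tail. The report could then print a difference of 0 with a zero-width interval, which reads as a precise finding of no effect, beside a real excess of low scores.

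**Working it through.** **Inputs.** The documents give no Apgar figures, so there is no planned Apgar result to reproduce. They do fix the size. The pain calculation (difference 0.3, SDs 0.85 and 1.23, alpha 5%, power 90%) reproduces at 263 per group with an unequal-variance t calculation; 263/0.90 is about 293, and the plan enrols 300. I use 300 per arm.

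The score distributions are assumptions. A low score here means any value below 8; only its rank matters, and no clinical cut-off is implied. Assume 15 low scores on esketamine and 3 on control.

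**Risk difference.** 15/300 − 3/300 = 5.0% − 1.0% = 4.0%. The Wilson limits are 3.05% to 8.08% and 0.34% to 2.90%. Newcombe interval:
- lower: 4.0 − √[(5.0 − 3.05)² + (2.90 − 1.0)²] = 1.3%
- upper: 4.0 + √[(8.08 − 5.0)² + (1.0 − 0.34)²] = 7.2%

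Fisher p = 0.007.

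**Hodges-Lehmann, other scores split about 70/25/5 over 10/9/8.** Counts at 10/9/8/low are 200/71/14/15 on esketamine and 208/74/15/3 on control. Of the 300 × 300 = 90,000 pairwise differences:
- negative: 71×208 + 14×282 + 15×297 = 23,171 (25.7%)
- positive: 200×92 + 71×18 + 14×3 = 19,720 (21.9%)
- zero: the remaining 47,109 (52.3%)

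The rank-based 95% limits lie at positions 45,000 ± 1.96 × √(90,000 × 601/12) = 45,000 ± 4,161, about the 45.4th and 54.6th percentiles of the differences. Both are zero, as is the median: the result is 0 (0 to 0). The lower limit leaves zero only if about 45% of pairs are negative. Median and IQR are 10 (9 to 10) in both arms.

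**Mann-Whitney on the same data.** z = (positive − negative)/2 ÷ SD, with SD² = (300×300/12) × [601 − Σ(t³ − t)/(600×599)], where t is the total at each score.

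| Other scores | Numerator | Tied totals t | SD | z | p |
|---|---|---|---|---|---|
| All at 10 | (855 − 4,455)/2 = −1,800 | 582, 18 | 627 | −2.87 | 0.004 |
| About 70/25/5 | (19,720 − 23,171)/2 = −1,725.5 | 408, 145, 29, 18 | 1,740 | −0.99 | 0.32 |

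The numerator barely moves. The spread over 8 to 10 nearly triples the SD, and the tail signal is lost in it.

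**Range for 15 versus 3.** Mann-Whitney p is 0.08 at 95/5 over 10/9, 0.21 at 85/15, and 0.40 at 50/40/10 over 10/9/8. For 30 versus 3 it is 0.017 at 70/25/5 and 0.041 at 50/40/10, so the test does respond; the Hodges-Lehmann result is still 0 (0 to 0).

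**Simulation (2,000 trials per scenario, true low-score rates 1% versus 5%).** Fisher power is 77% to 80%. Mann-Whitney power is 87% if all others score 10, and 15% to 45% over five mixed distributions. At 70/25/5, 61% of trials combined Hodges-Lehmann 0 (0 to 0), Mann-Whitney p>0.05 and Fisher p<0.05.

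**The case against.** Mann-Whitney is a valid test for an ordinal score, and it is not blind to the tail. The more completely scores are tied at 10, the closer it comes to a comparison of low with not low, and the better it detects an excess. A reader might infer that the planned test would usually miss harm. The documents do not support that, because they give no Apgar distribution.

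Extreme examples are easy to build. With control at 270 tens and 30 nines, and esketamine at 270 tens, 18 nines and 12 sixes, p is 0.87, but only because every low score is taken from the nines. Against the same control arm, the same 12 versus 0 excess gives p=0.12 if the low scores are drawn proportionally (259/29/12), 0.098 if they come from the tens (258/30/12), and 0.009 with graded depression (250 tens, 32 nines, 6 eights, 12 sixes). With 98% of controls at 10 (294/6 versus 282/6/12), it is 0.011. This stands: the large p-value is conditional.

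A reader might also infer that neonatal harm goes unexamined. It does not. Ward admission has a rate difference with a 95% CI, umbilical vein pH is a secondary outcome, and severe adverse events are described. These are partial backstops, but none of them describes low Apgar.

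Finally, low scores may be too rare for a risk difference to say much. With 3 versus 0 the interval is −0.4% to 2.9%. Yet 0 versus 0 still gives about −1.3% to 1.3%, which states what is excluded; a zero-width Hodges-Lehmann interval does not.

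**Conclusion.** The concern holds for the effect measure and only conditionally for the test. In every top-clustered scenario tried at 300 per arm, including 10% versus 1% low scores, the Hodges-Lehmann result was 0 (0 to 0) and median and IQR did not separate the arms. For an assumed 15 versus 3 low scores, a 4.0% risk difference (1.3% to 7.2%), Mann-Whitney p ran from 0.004 to about 0.40 according to the assumed spread of the other scores. The conclusion rests on scores clustering at 9 to 10 and on about 300 analysed per arm.

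It does not follow that Mann-Whitney is wrong, that the Hodges-Lehmann estimate must be dropped, or that the trial would conceal harm. The gap is that no planned Apgar summary describes the lower tail. Apgar is a secondary outcome, but it bears on a safety question that the trial itself raises, so the addition should be made.

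**What to change.** In protocol 13.5.2.1 and the matching SAP item (the second 4.5.1, under heading 4.5.2), keep the Mann-Whitney test and the Hodges-Lehmann estimate. Add, separately for 1 and 5 minutes:

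- the number of newborns at each score, by arm;
- the risk difference with a Newcombe 95% CI for scores below one cut-off. The sponsor's clinicians choose the cut-off and it is written into the plan before unmasking, so that it cannot be picked from the data.

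This follows what protocol 13.5.2.2 already does for ward admission and uses scores already collected under protocol 7.2.5. The cost is a few more table rows, agreement on one cut-off, and wide intervals if low scores are rare.
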